## **4 Sample Size and Power Justification**

The initial sample size was calculated based on the treatment effect of 6.5 points with a standard deviation of 16.5 in the change from baseline to Week 12 in the CMAI total score, to achieve 89% power at a 2-sided alpha level of 0.05. The initial sample size was 300 total subjects randomized in a 2:1 ratio to brexpiprazole or placebo. The statistical assumption of the treatment effect of 6.5 points separation (for brexpiprazole versus placebo) is the same as that used for the two completed phase 3 AAD Trials 331-12-283 and 331-12-284.

To account for an empirical dropout rate of 12-13% (based on the two completed phase 3 AAD Trials 331-12-283 and 331-12-284) and a lack of compliance at one identified clinical site, an increment of at least 30 additional subjects will be needed to maintain the target power. The resulting sample size is about 330 total subjects randomized in a 2:1 ratio to brexpiprazole or placebo. Within the brexpiprazole arm, subjects will be further

randomized in a 1:2 ratio to 2 mg/day or 3 mg/day, to explore the efficacy, safety, and tolerability of 2 mg/day and 3 mg/day brexpiprazole versus placebo.

One IA will be conducted when approximately the first 255 subjects had an opportunity to complete (OTC) the 12-week trial. The conservative Bonferroni critical boundary will be used for the two-stage group sequential analysis. Specifically, the alpha allocated to the IA is 0.015 and the alpha left for the final analysis is 0.035, both two-sided. The two-stage group sequential test will attain a power of 87%.

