### 8.1.2 Method of the Primary Analysis

Mean change from baseline in CMAI total score will be analyzed using a restricted maximum likelihood (REML)-based repeated measures approach. The analysis will be performed by fitting the MMRM model with an unstructured (UN) variance-covariance structure in which the change from the baseline in CMAI total score (Week 2, 4, 6, 8, 10, 12) will be the dependent variable based on the OC data. The analysis will include treatment (brexpiprazole and placebo), trial center, visit week, and an interaction term of treatment by visit week as the fixed, categorical effects and include the interaction term of baseline CMAI total score by visit week as covariates. In case there is a convergence problem with the MMRM model with the UN variance-covariance matrix, the following structures will be used in the order of 1) heterogeneous Toeplitz (TOEPH), 2) heterogeneous autoregressive of order 1 (ARH1), and 3) heterogeneous compound symmetry (CSH) and the first variance-covariance structure converging to the best fit will be used as the primary analysis.

The Kenward-Roger approximation will be used to estimate denominator degree of freedom and adjust standard errors. The contrast (i.e., difference in least-square means between brexpiprazole and placebo) at the Week 12 visit will be estimated from the interaction term of treatment by visit week and will serve as the primary treatment comparison. The point estimate and the 95% confidence interval estimate of the contrast at the Week 12 visit will be reported. Significance test will be based on the contrast estimate at the Week 12 visit by using a two-sided 0.015 level for the interim analysis and a two-sided 0.035 level for the final analysis (when the trial does not stop at the interim analysis). Analysis will be implemented using the software Statistical Analysis System® (SAS® version 9.4 or later) procedure PROC MIXED.

If a structured variance-covariance is used, the empirical sandwich estimator of the standard error of the fixed effects parameters will be used in order to deal with possible model misspecification of the variance-covariance matrix.

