Small centers will be defined as centers that do not have at least one evaluable subject (evaluability with regard to the primary efficacy variable) in each treatment arm in the double-blind treatment period. All small centers will be pooled within region to form “pseudo centers” for the purpose of analysis according to the following algorithm. Small centers will be ordered from the largest to the smallest based on the number of evaluable subjects. The process will start by pooling the largest of the small centers with the smallest of the small centers until a non-small center is formed. This process will be repeated using the centers left out of the previous pass. In case of ties in center size, the center with the smallest center code will be selected. If any centers are left out at the end

[figure not shown]
of this process, they will be pooled with the smallest pseudo centers, or if no pseudo centers exist, they will be pooled with the smallest non-small center. The pooling of the small centers will be performed within each region (North America and Other).

The chosen MMRM analysis assumes missing data to be “missing at random” (MAR), which is a reasonable assumption in longitudinal clinical trials. However, the possibility of “missing not at random” (MNAR) data can never be ruled out. In order to further evaluate robustness of the primary results to the deviations from MAR assumptions, additional sensitivity analysis will be conducted. Sensitivity analyses based on selection model, pattern-mixture model, and/or shared parameter model will be performed in order to explore data missing mechanisms of MNAR and investigate the response profile of dropout reason.

In case of gross violations of the MMRM model assumptions, additional supportive analyses will be provided using the generalized version of the Cochran-Mantel-Haenszel (CMH) procedure (van Elteren test), controlling for trial site.

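### The supportive van Elteren test in SAP 8.1.2 controls for site only; leaving out baseline CMAI makes it less efficient than it need be, by an amount that depends on a correlation the plan does not give

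*SAP*

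**What the plan says.** SAP 8.1.2 defines the primary analysis as an MMRM of change in CMAI total score with treatment, centre, visit and treatment by visit. It will also "include the interaction term of baseline CMAI total score by visit week as covariates". Later in the same section, for the case where the model's assumptions are grossly violated, "additional supportive analyses will be provided using the generalized version of the Cochran-Mantel-Haenszel (CMH) procedure (van Elteren test), controlling for trial site". No baseline term is named for that test. The sentence also leaves open the outcome variable, the visit, and whether observed-case or LOCF data are used.

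SAP 5.1 admits a subject to the Efficacy Sample only with a baseline CMAI total score, so the covariate is available for everyone analysed. The testing hierarchy in SAP 8.6, and its reduced form in the multiplicity addendum, do not include the van Elteren test.

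**The concern.** A back-up analysis is most useful when it differs from the primary analysis only in the assumption that is in doubt. Here the doubt would concern the MMRM's distributional or model assumptions, yet the back-up also gives up the baseline adjustment, which is not in doubt. Two things follow if baseline CMAI predicts change.

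- The rank test has less power than a rank test that uses baseline, so a non-significant result is harder to read.
- A chance difference between arms in baseline CMAI is corrected in the primary model but not in the analysis meant to support it.

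Some correlation is to be expected, because change contains baseline with a negative sign. Using change as the outcome does not remove the dependence on baseline; regression to the mean produces it.

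**Working it through.** **Inputs.** SAP 4 assumes a "treatment effect of 6.5 points with a standard deviation of 16.5". "The initial sample size was 300 total subjects randomized in a 2:1 ratio to brexpiprazole or placebo", "to achieve 89% power at a 2-sided alpha level of 0.05". "The resulting sample size is about 330 total subjects randomized in a 2:1 ratio to brexpiprazole or placebo", with an "empirical dropout rate of 12-13"% behind the increase. The final two-sided level is 0.035 (SAP 8.1.2). About 80 sites are planned (Protocol 3.3), so about 330/80 ≈ 4 subjects per site before pooling. Two inputs are missing: r, and whether 16.5 is the SD before or after baseline adjustment.

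**The plan's own figure.** With 200 and 100 subjects, SE = 16.5 × √(1/200 + 1/100) = 2.021. Power at 0.05 = Φ(6.5/2.021 − 1.960) = Φ(1.257) = 89.6%. The stated 89% is reproduced.

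**Normal-theory size of the baseline effect.** Adjusting for baseline multiplies the residual SD by √(1 − r²). At 0.035 the critical value is 2.108. With 300 subjects, unadjusted power = Φ(3.217 − 2.108) = 86.6%. At r = 0.5 the adjusted SE is 2.021 × 0.866 = 1.750, and power = Φ(3.714 − 2.108) = 94.6%, a gap of 8.0 points.

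The table repeats this for 330 subjects and for 287 (330 × 0.87). A takes 16.5 as the unadjusted SD. B takes it as the residual SD.

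| r | N = 330, A / B | N = 287, A / B |
|---|---|---|
| 0 | 0 / 0 | 0 / 0 |
| 0.2 | 1.2 / 1.3 | 1.5 / 1.5 |
| 0.3 | 2.6 / 3.1 | 3.3 / 3.6 |
| 0.4 | 4.5 / 6.0 | 5.7 / 6.9 |
| 0.5 | 6.6 / 10.5 | 8.6 / 11.9 |

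(Power points lost by leaving baseline out, two-sided 0.035.)

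**Rank test against rank test.** The relevant comparison is site-only van Elteren against the same test on residuals from baseline. It was simulated with 288 evaluable subjects, 2:1, effect 6.5, SD 16.5 before adjustment, and level 0.035. With one-arm sites pooled, the gain was 0 points at r = 0, about 1 to 2 at r = 0.2, 2 to 5 at r = 0.3 and 8 to 11 at r = 0.5. This held for normal errors and for t errors with 3 degrees of freedom. Examples with unequal site sizes (1,200 replicates):

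| Errors | r | 30 sites: site only → adjusted | 60 sites: site only → adjusted |
|---|---|---|---|
| Normal | 0.3 | 78.4 → 82.3% | 74.1 → 78.2% |
| Normal | 0.5 | 78.9 → 87.8% | 71.4 → 82.5% |
| t, 3 df | 0.3 | 95.7 → 97.8% | 93.1 → 97.5% |
| t, 3 df | 0.5 | 91.6 → 99.2% | 89.8 → 98.8% |

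Rejection under the null with adjustment was 3.0 to 3.7% at nominal 3.5%. In the normal, 60-site, r = 0.5 case, 14.7% of simulated trials were significant only with adjustment and 3.6% only without it. Monte Carlo error is about 1 to 1.5 points. If 16.5 is already the residual SD, the gap at r = 0.5 is larger: about 11 to 14 points with normal errors in runs with 24 to 72 equal-sized sites.

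**What r could be.** If baseline and Week 12 scores have equal variance (an assumption) and correlation ρ, then |r| = √((1 − ρ)/2). So |r| = 0.2 needs ρ = 0.92, |r| = 0.3 needs ρ = 0.82, and |r| = 0.5 needs ρ = 0.50. A larger variance at Week 12 would lower |r|.

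**Other differences from the primary analysis.** At r = 0, where baseline is irrelevant, van Elteren on normal data still fell below the site-adjusted parametric model: 70% against 83% with 72 sites, and 77 to 80% against 84 to 86% with 24 to 36 sites. That loss comes from ranks and small strata.

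**The case against.** The strongest reply is that the test runs only after a gross violation of the MMRM assumptions, so power computed on normal data does not describe it. Much of this stands. Under t errors with 3 degrees of freedom and r from 0 to 0.3, site-only van Elteren had 90 to 97% power against 83 to 89% for a parametric ANCOVA with baseline. A reader might infer from normal-data powers in the 70s that the back-up is too weak to interpret; that does not follow for the settings that trigger it. What does not stand is that the baseline gain disappears: the adjusted rank test gains from heavy tails as well, and the gap between the two rank tests remains.

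A second reply is that a least-squares regression on baseline before ranking is itself sensitive to outliers. That is fair. Ranking baseline and change before the regression kept most of the gain and answers it.

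A third is that the analysis decides nothing. It supports the MMRM without replacing it, and departures from missing at random have their own sensitivity analyses in SAP 8.1.4. This stands and sets the weight of the point. Site-stratified van Elteren is also the SAP's method for CGI-I, so the choice is consistent within the plan.

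**Conclusion.** The point holds as a minor improvement. The back-up omits a covariate that the primary model uses and that every analysed subject has, so it gives up efficiency if baseline predicts change, and it leaves chance imbalance uncorrected. The loss against a baseline-adjusted rank test is about 0, 1 to 2, 2 to 5 and 8 to 11 points at r = 0, 0.2, 0.3 and 0.5. These figures rest on an assumed r, an SD of 16.5 before adjustment, 288 evaluable subjects and a two-sided level of 0.035.

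Three stronger readings are not supported.

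- A fixed loss of 4 to 10 points is not a property of the plan. It corresponds to choosing r of roughly 0.3 to 0.5, and the documents give no r.
- A disagreement between the two analyses could not be put down to baseline alone. They also differ in ranks against means, in very small site strata, and in a repeated-measures model under missing at random against an unstated data set.
- The trial's conclusion is not at risk, because the test is conditional, supportive and outside the hierarchy.

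**What to change.** In SAP 8.1.2, make the supportive non-parametric analysis a stratified rank ANCOVA of the Week 12 change in CMAI total score:

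1. Regress the ranks of change on the ranks of baseline CMAI, ignoring treatment.
2. Apply the van Elteren procedure to the residuals, stratified by the pooled centres already defined in SAP 8.1.2 and 10.2.
3. Show the site-only van Elteren test beside it.

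The same sentence should state whether observed-case or LOCF data are used.

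The cost is a sentence or two in the SAP, a few lines of code and one extra analysis. No new data are needed. The test is slightly less familiar, and it assumes a roughly linear relation between the ranks of baseline and change. The primary analysis, the alpha levels and the testing hierarchy do not change.

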### 8.1.3 Technical Computation Details for Primary Efficacy Analysis

- 1) For primary analyses at Week 12 during the double-blind treatment period, the following algorithm will be used for including subjects in the 12-week analysis.
  - a) All scheduled visits during the 12 weeks after randomization, regardless of compliance to trial assessment schedule, will be included in the 12-week analysis.
  - b) All early terminated (ET) visits before week 12 will be included according to visit window in the 12-week analysis.
  - c) All ET visits > 12 weeks after randomization and outside of visit window will not be included in 12-week analysis.
  - d) The week number for an ET visit will be calculated by (date of ET visit

Baseline is the CMAI total score at baseline (Day 0 visit).

#### 8.1.4 Sensitivity Analyses for the Primary Efficacy Endpoint

Traditionally the dropout mechanisms are divided into three types: (1) Missing Completely at Random (MCAR), in which the probability of dropout doesn't depend on the observed data and the missing data; (2) MAR, in which the probability of dropout depends on the observed data; and (3) MNAR, where the probability of dropout depends on the missing data and possibly the observed data.

Most of MNAR methods have treated all observations with dropout as if they fall within the same dropout type. In practice, we would find that different dropout reasons may be related to the outcomes in different ways, for example, detailed dropout reasons for this trial are: adverse events (AE), lost to follow-up, protocol deviation, sponsor discontinued trial, subject met (protocol-specified) withdrawal criteria, subject was withdrawn from participation by the investigator, and subject withdrew consent to participate. Dropout due to an AE may lead to MNAR dropout. Subject withdrew consent may also lead to MNAR dropout. However, it is debatable whether a dropout caused by subjects withdrew consent is MAR or MNAR. Except AE, and subject withdrew consent, all other dropout reasons may be assumed as either MCAR or MAR dropout.

As sensitivity analyses for MAR assumption, analyses for MNAR will be carried out. Pattern Mixture Models (PMM) based on Multiple Imputation (MI) with mixed missing data mechanisms will be used to investigate the response profile of dropout subjects by last dropout reason under MNAR mechanism for the following three scenarios:

- Dropout reasons due to AE as MNAR
- Dropout reasons due to either AE or subject withdrew consent as MNAR
- All dropouts as MNAR

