Neuropsychiatric symptoms, including agitation, are common features of Alzheimer's disease and related dementias. Over the course of the disease, nearly all patients with Alzheimer's dementia will likely experience neuropsychiatric symptoms.⁴ Although agitation has a long history of being recognized as an important clinical feature of Alzheimer's disease, a widely recognized definition has been lacking in literature until recently. In 2015, the provisional International Psychogeriatric Association (IPA) definition of agitation limited to patients with cognitive impairment was developed and requires: a) evidence of emotional distress; (b) one of 3 observable types of behaviors-excessive motor activity, verbal aggression, or physical aggression; (c) that the behavior causes excess disability; and (d) that the behaviors cannot be solely attributable to a suboptimal care environment or other disorder such as a psychiatric illness, a medical illness, or effects of a substance.⁵

Agitation can be present from the early stages and throughout the course of Alzheimer's disease, and symptoms usually become more consequential as the disease progresses. Agitation in Alzheimer's dementia (AAD) has been associated with more rapid cognitive decline and progression to severe dementia, loss of independence, and earlier death.^{6,7} Agitation is a leading cause of institutionalization for patients with Alzheimer's dementia; within care facilities, 40% to 60% of patients with Alzheimer's disease exhibit symptoms of agitation with and without aggression.⁸ The presence of agitation in subjects with Alzheimer's dementia places a significant burden not only on subjects and their caregivers but also on the healthcare system. Additionally, aggressive behaviors such as combativeness, destroying property, and being a danger to oneself and others are significant predictors of time to nursing home placement.⁹

Currently, there are no approved treatments in the US for the management of agitation in patients with Alzheimer's disease. In other countries, treatment for the indication is restricted to the treatment of persistent aggression for a short period of time (6 weeks). Without approved labeling, at best in current clinical practice, clinicians rely on

guidelines when prescribing pharmaceutical treatments for patients with AAD. 10,11,12 Proven effective, tolerable, and safe treatment is essential in addressing this serious unmet need.

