3.8.3.2 Documenting Reasons for Treatment Discontinuation

If a subject discontinues the trial prematurely, the reason must be fully evaluated and recorded appropriately in eSource. If the subject is being withdrawn because of an AE, the AE should be indicated as the reason for withdrawal.

All subjects have the right to withdraw at any time during treatment without prejudice. The investigator can discontinue a subject's participation in the trial at any time if medically necessary. In addition, subjects meeting any of the following criteria must be withdrawn from the trial:

• Occurrence of any AE, intercurrent illness, or abnormality in a laboratory assessment that, in the opinion of the investigator, warrants the subject's permanent withdrawal from the trial

- Treatment with a prohibited concomitant medication other than the use of appropriate medications for the treatment of AEs under direction of the investigator, unless allowed after discussion with and approval by the medical monitor
- Subject noncompliance, defined as refusal or inability to adhere to the trial schedule or procedures (see Section 3.12, Subject Compliance)
- At the request of the subject, caregiver, legally acceptable representative, investigator, sponsor, or regulatory authority
- Subject becomes pregnant (see Section 5.5)
- Subject cannot tolerate the assigned dose of brexpiprazole (or matching placebo)
- Subject develops clinically significant agitation per investigator's judgment that cannot be adequately treated with allowed medications and poses a potential safety risk to the subject or others
- Subject is lost to follow-up
- Subject transfers from an institutionalized setting to a non-institutionalized setting, or vice versa. In case of a brief hospitalization, determination of subject eligibility to stay in the trial must be made based on subject safety by the investigator and medical monitor.

The medical monitor should be contacted if the Sheehan-STS score is 3 or 4 on any one question 3 through 6 or 11 or if the Sheehan-STS score is 2 or higher on any one questions 1a, 7 through 10, or 12, or 18, or if suicide results in death.

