### 8.1.1 Primary Estimand

In order to support the primary objective of the trial, treatment effect will be estimated under hypothetical situation had no subjects discontinued early from treatment. Due to this strategy, the last collected efficacy assessment after premature trial discontinuation will be done only once at the Early Termination (ET) Visit. Every effort will be made to complete all the ET evaluations prior to administering any additional medications for the treatment of agitation or any other prohibited medications. In the case of terminal or lost to follow-up event, no ET evaluations would be expected, and only scheduled assessments performed before such an event would be used for the primary efficacy analysis. All collected efficacy assessments will be slotted as per the Visit Window Definition, and only one assessment per visit window will be used for the primary efficacy analysis. If there are multiple assessments available in the same window, the latest one will be used.

This trial seeks to clarify the efficacy of brexpiprazole in improving the CMAI total score in the idealistic scenario of full adherence to the assigned treatment in all subjects. In clinical trial practice, however, instances of non-adherence such as treatment discontinuation are likely to occur before the study endpoint (i.e., the Week 12 Visit for this trial). Given this consideration, the hypothetical estimand is the most appropriate for achieving the primary objective of the trial. The primary estimand is described by five attributes as follows.

- Target Population: Subjects with agitation associated with dementia of the Alzheimer's type who have met protocol inclusion/exclusion criteria

- Endpoint: Change from Baseline to Week 12 in the CMAI total score
- Intercurrent Events: Intercurrent events refer to premature treatment discontinuation (i.e., early dropout) prior to Week 12 attributable to adverse events or lack of efficacy or withdrawal of consent/assent or any other causes.
- Measure of Intervention effect: Difference in endpoint means between the brexipiprazole and placebo treatment arm.
- Treatment regimen: 2 or 3 mg daily for 12 weeks.

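### SAP 8.1.4 assumes that withdrawals coded as meeting withdrawal criteria or as investigator decisions are missing at random, so its reason-specific delta analyses give no shift to withdrawals for uncontrolled agitation

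*SAP*

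**What the plan says.** SAP 8.1.4 lists seven dropout reasons. Besides AE, loss to follow-up, protocol deviation and sponsor termination, they are "subject met (protocol-specified) withdrawal criteria, subject was withdrawn from participation by the investigator, and subject withdrew consent to participate". It regards AE as possibly MNAR and consent withdrawal as debatable, and disposes of the rest in one sentence: "Except AE, and subject withdrew consent, all other dropout reasons may be assumed as either MCAR or MAR dropout".

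Three MNAR scenarios follow: AE dropouts (1), AE or consent dropouts (2), and all dropouts (3). The delta method in the same section raises delta from 0 to 100% of 6.5 points and/or of the observed difference. Its step 3 adds delta only to treated subjects who left for AE or consent. A separate placebo-based imputation covers missing data in both arms whatever the reason.

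Protocol 3.8.3.2 lists the criteria for mandatory withdrawal. One reads: "Subject develops clinically significant agitation per investigator's judgment that cannot be adequately treated with allowed medications", with a safety risk to the subject or others. Others are "Subject cannot tolerate the assigned dose of brexpiprazole (or matching placebo"), use of a prohibited medication, and "Subject transfers from an institutionalized setting to a non-institutionalized setting, or vice versa". The same section has AE-driven withdrawals recorded under the AE. Protocol 5.2 makes worsening of the condition an AE only when its features are unusual or severe. SAP 8.1.1 defines the intercurrent events as "premature treatment discontinuation (i.e., early dropout) prior to Week 12 attributable to adverse events or lack of efficacy", among other causes.

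**The concern.** Agitation that allowed medication cannot control is failure on the construct the CMAI measures. Such a subject would usually not be coded AE and has no lack-of-efficacy code to go to, although the estimand names that cause. The likeliest destinations are the withdrawal-criteria code and the investigator-withdrawal code, and SAP 8.1.4 assumes both to be MCAR or MAR.

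The reason-specific scenarios exist to ask what happens if outcome-related dropouts did worse than MAR predicts. If they shift AE and consent withdrawals but leave treatment failures at the MAR value, the reason-specific tipping delta looks larger, and the result sturdier, than it should.

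**Working it through.** **Which analysis reaches a drug-arm withdrawal for uncontrolled agitation, coded under one of the two reasons?**

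- Scenario 1 (AE): not reached.
- Scenario 2 (AE or consent): not reached.
- Scenario 3 (all dropouts): reached by its title, but step 3 names only AE and consent, so no delta is assigned as written. Step 3 fits scenario 2 alone.
- Placebo-based imputation: reached, but not separated by reason. By the SAP's own description, benefit before dropout is carried into the imputed values and fades over time.

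**The plan's own figures.** SAP section 4 gives an effect of 6.5, SD 16.5, 2:1 allocation, 300 subjects and 89% power at two-sided 0.05.

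- SE = 16.5 × √(1/100 + 1/200) = 2.02, and power = 0.8955, consistent with 89%.
- The group-sequential power of 87% also reproduces: 0.858 to 0.871 with 289 to 300 evaluable subjects at the final analysis.

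**Size of the gap.** Inputs from SAP section 4: about 330 subjects at 2:1, so 330 × 2/3 = 220 on drug, and dropout of 12-13% (midpoint 12.5%). The same rate in both arms is assumed. The share of dropouts carrying the two codes is not in the documents; 20% to 50% is assumed.

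- Drug-arm dropouts: 220 × 0.125 = 27.5.
- Carrying the two codes: 27.5 × 0.20 = 5.5, up to 27.5 × 0.50 = 13.75.
- Unshifted amount at delta 6.5 = subjects × 6.5 / 220: 5.5 × 6.5 / 220 = 0.16, up to 13.75 × 6.5 / 220 = 0.41 points.
- All drug-arm dropouts shifted: 0.125 × 6.5 = 0.81 points.

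**Against the precision of the trial.** With 330 × 0.875 ≈ 289 evaluable subjects, SE = 16.5 × √(4.5/289) = 2.06. The gap is therefore 0.16/2.06 = 0.08 to 0.41/2.06 = 0.20 of an SE. At the final two-sided level of 0.035 (z = 2.108) the boundary is 2.108 × 2.06 ≈ 4.34 points, or 4.06 if all 330 were evaluable.

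**When it changes the answer.** Take every other dropout as AE or consent, use the 289-subject boundary, and ignore any change in variance from imputation.

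- At a 50% share, step 3 as written shifts 0.81 − 0.41 = 0.40 points. An observed difference between about 4.34 + 0.40 = 4.74 and 4.34 + 0.81 = 5.15 would survive it but fail once the two codes are added.
- At a 20% share the shift is 0.81 − 0.16 = 0.65, and the window narrows to about 4.99 to 5.15.

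**Tipping delta.** On the same assumption, the delta needed to overturn the result is overstated by 1/(1 − share): 1/0.8 = 1.25 to 1/0.5 = 2.0.

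All these sizes count every subject with either code. Both codes also hold unrelated withdrawals, so the part due to agitation is smaller.

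**The case against.** **These dropouts are already covered.** Scenario 3 is meant to shift everyone, placebo-based imputation ignores reason, and SAP 8.1.2 also names selection, pattern-mixture and/or shared-parameter models. Applied to all treated dropouts, scenario 3 shifts more subjects than any narrower set. This stands in large part: a reader might infer that the plan never tests these dropouts, and that is not so. What remains is that the reason-specific scenarios miss them, and that scenario 3 lacks a written delta step.

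**Endpoint-related is not the same as MNAR.** CMAI is rated every two weeks. An early-termination rating is sought before other agitation medication, and SAP 8.1.3 slots it into the analysis. If the worsening is observed, MAR is defensible, and the SAP's wording is only permissive. This stands as a reason not to call these dropouts MNAR outright. It does not explain the asymmetry, because AE and consent withdrawals have the same early-termination visit and are still stressed.

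**Some failures may be coded elsewhere.** Protocol 3.8.3.1 allows a dissatisfied subject to initiate discontinuation, which could be coded as consent withdrawal and so fall in scenario 2. That is possible for some, but it does not fit withdrawals required by the agitation criterion.

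**Other criteria on the list.** A reader might infer that intolerance, change of setting and prohibited medication are all misclassified too. The documents do not support that:

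- AE-driven intolerance is coded AE and is already in scenarios 1 and 2.
- The transfer criterion runs in both directions. The Protocol introduction does say "Agitation is a leading cause of institutionalization for patients with" Alzheimer's dementia, but that concerns one direction only.
- Prohibited medications include CYP inhibitors with no bearing on agitation (Protocol Table 4.1-2).

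**Conclusion.** The point holds in a limited form. The blanket MCAR/MAR assumption is not justified for two codes that can contain withdrawals for uncontrolled agitation, and scenarios 1 and 2 and delta step 3 give those subjects no shift. The coding route is inferred from the protocol's AE rule and the missing lack-of-efficacy code; the documents show no coding conventions beyond that.

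The size is modest: 0.16 to 0.41 points at delta 6.5, resting on an assumed 20-50% share and equal dropout in the arms. It would matter only for a result near the boundary, which is also where a tipping-point analysis is informative. The primary test, alpha allocation and estimand are untouched.

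Two stronger conclusions are tempting. One is that the primary result as a whole will look more robust than it is; scenario 3, once its delta step is written, and placebo-based imputation argue against that. The other is that the omitted dropouts are the ones most tied to the endpoint; that is reasonable for uncontrolled agitation, but without a breakdown by reason it cannot be said of the two codes in general.

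**What to change.** In SAP 8.1.4, before the final unblinding:

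1. Remove the withdrawal-criteria and investigator-withdrawal codes from the sentence that assumes MCAR or MAR.
2. Extend scenario 2, or add a scenario between 2 and 3, so that withdrawals for uncontrolled or worsening agitation, including those for prohibited medication given for agitation, are MNAR together with AE and consent. Where the recorded reason cannot separate them, include both codes in full.
3. Rewrite delta step 3 so that delta goes to the dropouts named in each scenario: AE only in scenario 1, the scenario 2 set in scenario 2, and all treated dropouts in scenario 3.
4. Leave AE-driven intolerance under AE. Do not class every change of setting or every prohibited medication as outcome-related.

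The cost is SAP wording and a changed list of reason codes in a program already planned. The sensitivity results may be slightly less favourable. Where both codes have to be included in full, some unrelated withdrawals, such as noncompliance, will be shifted too.
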